### **10.3.2 Permanent treatment discontinuation with investigational medicinal product(s)**

Permanent treatment discontinuation is any treatment discontinuation associated with the definitive decision from the Investigator or the patient not to re-expose the patient to the IMP at any time.

### **10.3.3 List of criteria for permanent treatment discontinuation**

Patients may withdraw from treatment with the IMP at any time for any reason or this may be the Investigator's decision. Patients should discuss stopping study medication with the site before doing so in order that questions can be addressed, glycemic therapy adjusted, and a follow-up assessment arranged. All efforts should be made to document the reasons for treatment discontinuation and this should be documented in the e-CRF.

The following reasons lead to permanent discontinuation:

- At the patient's own request (ie, withdrawal of consent for treatment).
- If, in the Investigator's opinion, continuation with the administration of the study treatment would be detrimental to the patient's well-being.
- Intercurrent condition that requires permanent discontinuation of the study treatment as long as the abnormality persists and if the casual relationship of the concerned event and the IMP is possible (according to the Investigator's best medical judgment).
- Pregnancy (in female patients).
- Specific request of the Sponsor.

Any abnormal laboratory value will be immediately rechecked to confirm the result before a decision is made to permanently discontinue IMP for the concerned patient.

For patients who prematurely discontinue the IMP, the assessments planned at the EOT visit (see Section 10.1.2.4) will be performed as soon as possible after treatment discontinuation. The reason(s) for IMP discontinuation will be clearly specified. This EOT assessment may occur at a regularly scheduled or unscheduled visit.

#### **10.3.4 Handling of patients after permanent treatment discontinuation**

Every effort should be made to maintain patients in the study. Patients should be followed-up according to the study procedures specified in this protocol up to the scheduled date of study completion, or up to recovery or stabilization of any AE to be followed-up as specified in this protocol, whichever comes later.

If a patient decides to discontinue IMP early, a Premature EOT visit (see Section 10.1.2.4) should be scheduled prior to treatment discontinuation, if possible. If not possible, the Premature EOT visit should be scheduled as soon as possible after treatment discontinuation. For patients that discontinue treatment but remain in the study, remaining study visits should occur as scheduled where possible. The IRT should be notified of EOT.

After permanent treatment discontinuation, of the investigational products, any treatments (other than SGLT2 inhibitors) are permitted, as deemed necessary by the Investigator.

All confirmed cases of permanent treatment discontinuation should be recorded by the Investigator in the appropriate pages of the e-CRF.

#### **10.3.5 Procedure and consequence for patient withdrawal from study**

Patients may withdraw from the study before study completion if they decide to do so, at any time and irrespective of the reason. Withdrawal of consent for treatment should be distinguished from withdrawal of consent for follow-up visits and from withdrawal of consent for non-patient contact follow-up, eg, medical records check. Patients will be told that they are free to withdraw from the study at any time without any adverse effect on their care. However, if they no longer wish to take the IMP, they will be encouraged to remain in the study and attend the remaining study visits. The value of all their study data collected during their continued involvement will be emphasized as important to the public health value of the study.

If possible, the patients are assessed using the procedure normally planned for the EOT visit.

Patients who withdraw should be explicitly asked about the contribution of possible AEs to their decision to withdraw consent, and any AE information elicited should be documented. Preferably the patient should withdraw consent in writing and, if the patient or the patient's representative refuses or is physically unavailable, the site should document and sign the reason for the patient's failure to withdraw consent in writing.

All confirmed study withdrawals should be recorded by the Investigator in the appropriate screens of the e-CRF and in the patient's medical records. In the medical record, at least the date of the withdrawal and the reason should be documented.

For patients who fail to return to the site, unless the patient withdraws consent for follow-up, the Investigator should make the best effort to re-contact the patient (eg, contact patient's family or private physician, review available registries or health care databases), and to determine his/her health status, including at least his/her vital status. Attempts to contact such patients must be documented in the patient's records (eg, times and dates of attempted telephone contact, receipt for sending a registered letter).

Patients who have withdrawn from the study cannot be re-randomized (treated) in the study. Their inclusion and treatment numbers must not be reused.

## **10.4 OBLIGATION OF THE INVESTIGATOR REGARDING SAFETY REPORTING**

### **10.4.1 Definitions of adverse events**

#### **10.4.1.1 Adverse event**

An **AE** is any untoward medical occurrence in a patient or clinical investigation patient administered a pharmaceutical product and which does not necessarily have to have a causal relationship with this treatment.

#### **10.4.1.2 Serious adverse event**

A **SAE** is any untoward medical occurrence that at any dose:

- Results in death, or
- Is life-threatening, or
- **Note:** The term "life-threatening" in the definition of "serious" refers to an event in which the patient was at risk of death at the time of the event; it does not refer to an event which hypothetically might have caused death if it were more severe.
- Requires inpatient hospitalization or prolongation of existing hospitalization or
- Results in persistent or significant disability/incapacity or
- Is a congenital anomaly/birth defect
- Is a medically important event

Medical and scientific judgment should be exercised in deciding whether expedited reporting is appropriate in other situations, such as important medical events that may not be immediately life-threatening or result in death or hospitalization but may jeopardize the patient or may require medical or surgical intervention (ie, specific measures or corrective treatment) to prevent one of the other outcomes listed in the definition above.

**Note:** The following list of medically important events is intended to serve as a guideline for determining which condition has to be considered a medically important event. The list is not intended to be exhaustive:

- Intensive treatment in an emergency room or at home for:
  - Allergic bronchospasm
  - Blood dyscrasias (ie, agranulocytosis, aplastic anemia, bone marrow aplasia, myelodysplasia, pancytopenia, etc)
  - Convulsions (seizures, epilepsy, epileptic fit, absence, etc)
- Development of drug dependence or drug abuse.
- ALT >3 times ULN + total bilirubin >2 times ULN or asymptomatic ALT increase >10 times ULN.
- Suicide attempt or any event suggestive of suicidality.
- Syncope, loss of consciousness (except if documented as a consequence of blood sampling).
- Bullous cutaneous eruptions.
- Cancers diagnosed during the study or aggravated during the study.
- Chronic neurodegenerative diseases (newly diagnosed) or aggravated during the study.

#### **10.4.1.3 Adverse event of special interest**

An AESI is an AE (serious or non-serious) of scientific and medical concern specific to the Sponsor's product or program, for which ongoing monitoring and rapid communication by the Investigator to the Sponsor may be appropriate. Such events may require further investigation in order to characterize and understand them. AESIs may be added or removed during a study by protocol amendment.

The AESI for this study are:

- Pregnancy of a female patient entered in a study as well as pregnancy occurring in a female partner of a male patient entered in a study with IMP/NIMP:
  - Pregnancy occurring in a female patient included in the clinical trial or in a female partner of a male patient entered in the clinical trial. It will be qualified as an SAE only if it fulfills one of the seriousness criteria (see Section 10.4.1.2).
  - In the event of pregnancy in a female patient, IMP should be discontinued.
  - Follow-up of the pregnancy in a female patient or in a female partner of a male patient is mandatory until the outcome has been determined (see Appendix A).
- Symptomatic overdose with IMP/NIMP:
  - A symptomatic overdose (accidental or intentional) with the IMP/NIMP is an event suspected by the Investigator or spontaneously notified by the patient and resulting in clinical symptoms and/or signs accompanied by administration of more than twice the intended daily dose within a 24-hour period. It will be recorded in the e-CRF as an AESI with immediate notification "Symptomatic OVERDOSE (accidental or

intentional)” in all cases and will be qualified as an SAE only if it fulfills the SAE criteria.

- **Note:** an asymptomatic overdose with the IMP/NIMP, accidental or intentional, is defined as administration of more than twice the intended daily dose within a 24-hour period, without clinical symptoms and/or signs, either suspected by the Investigator or spontaneously notified by the patient, not based on accountability assessment. It will be recorded as AE “Asymptomatic OVERDOSE, accidental or intentional”.
- ALT increase >3 times ULN (refer to related flowchart, Appendix D).

#### **10.4.1.4 Events of special interest**

An EOSI is a serious or non-serious AE of scientific and medical concern specific to the Sponsor’s product or program, for which ongoing monitoring may be appropriate. Such events may require further investigation in order to characterize and understand them. These events should be reported on the specific e-CRF page and will only qualify for expedited reporting when serious (fulfilling SAE criteria).

The EOSI for this study are:

- Major adverse cardiovascular events (MACE [CV death, MI, or stroke]) and other specific CV events (eg, heart failure leading to hospitalization)
- Severe hypoglycemia (see Section 9.2.1.2)
- Genital mycotic infections (to include vulvovaginal candidiasis in females and candida balanitis in males)
- UTIs
- Clinically relevant volume depletion and events related/possibly related to volume depletion
- Diarrhea
- Pancreatitis
- Bone fractures
- VTE to include deep venous thrombosis and thromboembolism (to include pulmonary embolism)
- DKA
- Renal events to include 50% decline in eGFR, end stage kidney disease, renal death
- Malignancies of special interest (breast, bladder, renal cell, Leydig cell, pancreatic, prostate, and thyroid carcinoma)
- Adverse events leading to amputation

#### **10.4.2 General guidelines for reporting adverse events**

- All AEs, regardless of seriousness or relationship to IMP/NIMP, spanning from the signature of the ICF until the end of the study as defined by the protocol for that patient, are to be recorded on the corresponding page(s) or screen(s) of the e-CRF.
- Whenever possible, diagnosis or single syndrome should be reported instead of symptoms. The Investigator should specify the date of onset, intensity, action taken with respect to IMP, corrective treatment/therapy given, additional investigations performed, outcome, and his/her opinion as to whether there is a reasonable possibility that the AE was caused by the IMP or by the study procedure(s).
- In this study, the use of concomitant medications including antidiabetic medications may make it difficult to assess the causal relationship, particularly for hypoglycemia. The Global Safety Officer with input from other appropriate study team members will determine the causal relationship when it is not clearly provided by the Investigator.
- The Investigator should take appropriate measures to follow all AEs until clinical recovery is complete and laboratory results have returned to normal, or until progression has been stabilized, or until death, in order to ensure the safety of the patients. This may imply that observations will continue beyond the last planned visit per protocol, and that additional investigations may be requested by the monitoring team up to as noticed by the Sponsor.
- When treatment is prematurely discontinued, the patient's observations will continue until the end of the study as defined by the protocol for that patient.
- Laboratory, vital signs, or ECG abnormalities are to be recorded as AEs if they are medically relevant based on the investigator's medical judgment, eg,:
  - Symptomatic and/or
  - Requiring either corrective treatment or consultation, and/or
  - Leading to IMP discontinuation or modification of dosing, and/or
  - Fulfilling a seriousness criterion, and/or
  - Defined as an AESI or EOSI

#### **10.4.3 Instructions for reporting serious adverse events**

In the case of occurrence of an SAE, the Investigator or any designees must immediately:

- ENTER (within 24 hours) the information related to the SAE in the appropriate screens of the e-CRF; the system will automatically send a notification to the Monitoring team and Pharmacovigilance after approval of the Investigator within the e-CRF.
- SEND (preferably by fax or e-mail) a photocopy of all examinations carried out and the dates on which these examinations were performed, to the representative of the monitoring team whose name, fax number, and e-mail address appear on the clinical trial protocol. Care should be taken to ensure that the patient's identity is protected and the patient's identifiers in the clinical trial are properly mentioned on any copy of a source document provided to the Sponsor. For laboratory results, include the laboratory normal ranges.

- All further data updates should be recorded in the e-CRF as appropriate, and further documentation as well as additional information (for laboratory data, concomitant medications, patient status, etc) should be sent (by fax or e-mail) to the monitoring team within 24 hours of knowledge of the SAE. In addition, every effort should be made to further document any SAE that is fatal or life-threatening within a week (7 days) of the initial notification.
- A back-up plan (using a paper case report form [CRF] process) is available and should be used when the e-CRF system does not work.

Any SAE brought to the attention of the Investigator at any time after the end of the study for the patient and considered by him/her to be caused by the IMP with a reasonable possibility should be reported to the monitoring team.

#### **10.4.4 Guidelines for reporting adverse events of special interest**

For AESIs, the Sponsor must be informed immediately (ie, within 24 hours), as per SAE notification guidelines described in Section 10.4.3, even if not fulfilling a seriousness criterion, using the corresponding pages of the CRF (to be sent) or screens in the e-CRF.

#### **10.4.5 Guidelines for reporting events of special interest**

If an EOSI fulfills the criteria of an SAE, reporting should be performed according to the instructions for reporting of SAEs (see Section 10.4.3). Otherwise, reporting should follow the instructions for an AE (see Section 10.4.2).

#### **10.4.6 Guidelines for management of specific laboratory abnormalities**

Decision trees for the management of certain laboratory abnormalities by Sanofi are provided in Appendix D.

The following laboratory abnormalities should be monitored, documented, and managed according to the related flow chart in protocol appendices.

- Neutropenia
- Thrombocytopenia
- Increase in ALT
- Acute renal insufficiency
- Suspicion of rhabdomyolysis

### **10.5 OBLIGATIONS OF THE SPONSOR**

During the course of the study, the Sponsor will report in an expedited manner:

- All SAEs that are both unexpected and at least reasonably related to the IMP (SUSARs), to the regulatory authorities, independent ethics committee (IECs)/institutional review boards (IRBs) as appropriate and to the Investigators.

- All SAEs that are expected and at least reasonably related to the IMPs to the regulatory authorities, according to local regulations.
- The following AESIs to those regulatory authorities who require such reporting:
  - Pregnancy
  - Symptomatic overdose
  - ALT increase >3 times ULN

Adverse events that are considered expected will be specified by the reference safety information provided in the current IB.

If required, unblinding of SUSARs will be the responsibility of the Sponsor.

The Sponsor will report all safety observations made during the conduct of the trial in the CSR.

## **10.6 SAFETY INSTRUCTIONS**

[figure not shown]
### **10.6.1 Hypoglycemia**

During the study, patients are instructed to document any hypoglycemic episodes in their study diary. The hypoglycemia will be reported in the specific e-CRF page with onset date and time, symptoms and/or signs, the SMBG value if available, and the treatment. If the event fulfills SAE criteria, hypoglycemia will also be reported as an SAE.

Hypoglycemia is categorized according to the ADA workgroup on hypoglycemia classification (15) and summarized in Figure 1.

In addition to the threshold of  $\leq 70$  mg/dL ( $\leq 3.9$  mmol/L), hypoglycemia episodes with a plasma glucose of  $< 54$  mg/dL ( $< 3.0$  mmol/L) will be analyzed separately.

**Figure 1 - Hypoglycemia classification in Study EFC14838**

\*The patient is not able to treat her/himself because of the acute neurological impairment and requires another person to actively administer sugar, glucagon or intravenous glucose

PG: plasma glucose; SAE: serious adverse event.

### ***Severe hypoglycemia***

Severe hypoglycemia is an event requiring assistance of another person to actively administer carbohydrate, glucagon, intravenous glucose or other resuscitative actions. These episodes may be associated with sufficient neuroglycopenia to induce seizure, unconsciousness or coma. Self-monitored plasma glucose values may not be available, but neurological recovery attributable to the restoration of plasma glucose to normal is considered sufficient evidence that the event was induced by a low plasma glucose concentration.

**Note:** “requiring assistance of another person” means that the patient could not help himself or herself to treat the hypoglycemia. Assisting a patient out of kindness, when assistance is not required, should not be considered a “requires assistance” incident.

Any hypoglycemic event which leads to unconsciousness, coma, or seizure should also be reported as an SAE.

### ***Documented symptomatic hypoglycemia***

Documented symptomatic hypoglycemia is an event during which typical symptoms of hypoglycemia accompanied by a measured plasma glucose concentration of  $\leq 3.9$  mmol/L ( $\leq 70$  mg/dL).

Clinical symptoms that are considered to result from a hypoglycemic episode are for example increased sweating, nervousness, asthenia/weakness, tremor, dizziness, increased appetite, palpitations, headache, sleep disorder, confusion, seizures, unconsciousness, or coma.

### ***Asymptomatic hypoglycemia***

Asymptomatic hypoglycemia is an event not accompanied by typical symptoms of hypoglycemia but with a measured plasma glucose concentration  $\leq 3.9$  mmol/L ( $\leq 70$  mg/dL).

**Note:** low plasma glucose values without symptoms or signs should not be reported more than once within 30 minutes. Repeated low glucose values within a short period could be due to malfunction of the device, error testing, or following up a low glucose reading. The Investigator should try not to document false low SMBG values or redundant low glucose values as asymptomatic hypoglycemic events. Further clarification with the patients is needed.

### ***Probable symptomatic hypoglycemia***

Probable symptomatic hypoglycemia is an event during which symptoms of hypoglycemia are not accompanied by a plasma glucose determination (but that was presumably caused by a plasma glucose concentration  $\leq 3.9$  mmol/L [ $\leq 70$  mg/dL]), ie, symptoms treated with oral carbohydrate **without** a test of plasma glucose.

### ***Relative hypoglycemia***

Relative hypoglycemia, recently termed “pseudo-hypoglycemia” (15), is an event during which the patient reports typical symptoms of hypoglycemia, and interprets the symptoms as indicative of hypoglycemia, but with a measured plasma glucose concentration  $> 3.9$  mmol/L ( $> 70$  mg/dL).

## **10.7 ADVERSE EVENTS MONITORING**

All events will be managed and reported in compliance with all applicable regulations, and included in the final CSR.

## 11 STATISTICAL CONSIDERATIONS

### 11.1 DETERMINATION OF SAMPLE SIZE

The sample size/power calculations were performed based on the primary endpoint of the change of HbA1c from Baseline to Week 52 in the intent-to-treat (ITT) population. Assuming a common standard deviation (SD) of 1.1%, and the true difference between sotagliflozin 400 mg and glimepiride is zero, 310 patients in the sotagliflozin 400 mg and glimepiride groups will ensure that the upper bound of the 2-sided 95% confidence interval (CI) of the adjusted mean difference is below 0.3% with at least 90% power. This sample size will have 80% power to test the non-inferiority of the change of HbA1c from Baseline to Week 52 in completers, with 30% dropout rate.

A sample size of 310 patients in sotagliflozin 400 mg group and 155 patients in placebo group will have >99% power to detect a treatment difference of 0.6% in mean HbA1c change from Baseline to Week 26 between sotagliflozin 400 mg and placebo (SD 1.2%; 2-sided 5% significance level).

A sample size of 155 patients in sotagliflozin 200 mg group and 155 patients in placebo group will have 95% power to detect a treatment difference of 0.5% in mean HbA1c change from Baseline to Week 26 between sotagliflozin 200 mg and placebo (SD 1.2%; 2-sided 5% significance level).

The total sample size will be 930 patients to be randomized (sotagliflozin 400 mg group: 310; sotagliflozin 200 mg group: 155; glimepiride: 310; placebo: 155).

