### **4.3 RATIONALE FOR SELECTION OF DOSES**

The selection of 400 mg and 200 mg once daily doses is based on the results of the Phase 2b dose-ranging study LX4211.1-202-DM. In this study sotagliflozin doses of 75 mg once daily, 200 mg once daily, 200 mg twice daily, and 400 mg once daily were tested over a 12-week, double-blind period. The sotagliflozin 400 mg and 200 mg once daily doses were chosen for further evaluation based on their HbA1c lowering effects and the overall safety and tolerability observed at these doses. At 12 weeks, the sotagliflozin 400 mg dose lowered HbA1c by a mean of 0.93% and the 200 mg dose lowered HbA1c by a mean of 0.48%, while placebo lowered HbA1c by a mean of 0.14%. The other doses did not have any advantages in efficacy, safety, or tolerability.

The overall incidence of AEs in patients receiving sotagliflozin 400 mg or 200 mg once daily was similar to that seen with placebo.

In healthy subjects sotagliflozin was well-tolerated following single doses up to 2000 mg, and in multiple doses up to 800 mg over 10 days. Furthermore, in a thorough QT study, single doses of sotagliflozin (800 mg and 2000 mg) were well-tolerated and did not prolong the QT interval. Additionally, evaluation of metabolites in urine and plasma of healthy subjects resulted in no safety concerns following single doses of 400 mg sotagliflozin. Single doses of sotagliflozin 400 mg in combination with sitagliptin, and multiple doses of sotagliflozin up to 400 mg in combination with metformin over 12 weeks were also well-tolerated in patients with T2D.

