One Patient Reported Outcome (PRO) will be assessed in this study. The Patient Qualitative Assessment of Treatment (PQAT) will be assessed at Week 26 and at the final on-treatment visit (Week 52). This instrument includes a 7-point Likert Scale for the patient to evaluate his/her subjective response to the treatment (-3 to +3 including 0 for a neutral response) and 2 free-text response questions to describe key advantages and disadvantages.

Safety, tolerability, pharmacokinetics (PK), and pharmacodynamic (PD) effects of sotagliflozin are supported by Phase 1 and Phase 2 studies and toxicology data in rats up to 26 weeks and dogs up to 39 weeks as well as 2-year carcinogenicity data in rats. These data support the use of 400 mg and 200 mg once-daily doses as safe and effective.

To achieve balanced randomization for assessment of the primary endpoint, randomization will be stratified based on preexisting metabolic control (baseline HbA1c  $\leq 8.5\%$  versus  $>8.5\%$ ). Another stratification factor (SBP  $<130$  mmHg versus  $\geq 130$  mmHg) has been added to ensure balance in randomization for a secondary endpoint (change from Baseline to 12 weeks in SBP for patients with baseline SBP  $\geq 130$  mmHg).

A parallel-group, randomized active-, and placebo-controlled and double-dummy study was selected because trial participants are exposed to a single treatment and assignment to that treatment is based solely on chance. This design is free of the limitations of competing designs such as crossover in which there may be a carryover of effect from one treatment to the second treatment. Although this carryover effect can be minimized with a washout period, it is possible that some longer term effects may persist. While the sample size of the parallel-group design is larger to account for more variability when participants cannot serve as their own control, the above mentioned limitations of the crossover design have led the randomized controlled trial design to be the standard for therapeutic confirmatory trials for regulatory approval such as this trial.

Patients will be randomized in 2:1:2:1 ratio and any potential bias will be minimized by blinding the patients, the Investigators, and the Sponsor to the treatment allocations, and by adjudicating the endpoints in a blinded fashion.

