#### **11.4.2.4 Multiplicity considerations**

To control for the family-wise Type I error, a fixed-sequence testing procedure will be applied to the primary and secondary endpoints to the following order:

The primary endpoint of the HbA1c change from Baseline to Week 52 comparing sotagliflozin 400 mg versus glimepiride will be tested at  $\alpha = 0.025$  (1-sided) using a non-inferiority margin of 0.3% of HbA1c change. Once the non-inferiority is declared (the upper bound of the 2-sided 95% CI of the adjusted mean difference between sotagliflozin 400 mg and glimepiride is  $< 0.3\%$ ), a hierarchical testing procedure will be performed to test the following key secondary endpoints by the following prioritized order. The testing will stop as soon as an endpoint is found to be not statistically significant at  $\alpha = 0.05$  (2-sided):

- The superiority of sotagliflozin 400 mg compared to glimepiride on:
  - Change in body weight from Baseline to Week 52
  - Change in SBP from Baseline to Week 12 in patients with baseline SBP  $\geq 130$  mmHg
  - Change in SBP from Baseline to Week 12 in all patients
  - The proportion of patients with at least 1 documented symptomatic hypoglycemic event ( $\leq 70$  mg/dL) during the 52-week Treatment Period
- The superiority of sotagliflozin 400 mg compared to placebo on the change in HbA1c from Baseline to Week 26
- The superiority of sotagliflozin 200 mg compared to placebo on the change in HbA1c from Baseline to Week 26
- The superiority of sotagliflozin 400 mg compared to placebo on:
  - Change in body weight from Baseline to Week 26
  - Change in SBP from Baseline to Week 12 in patients with baseline SBP  $\geq 130$  mmHg

- Change in SBP from Baseline to Week 12 in all patients
- The non-inferiority of sotagliflozin 200 mg compared to glimepiride on the change in HbA1c from Baseline to Week 52
- The superiority of sotagliflozin 400 mg compared to glimepiride on the change in HbA1c from Baseline to Week 52

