1.3 DETERMINATION OF SAMPLE SIZE

The sample size/power calculations were performed based on the primary endpoint of change of HbA1c from Baseline to Week 52 in the intent-to-treat (ITT) population. Assuming a common standard deviation (SD) of 1.1%, and the true difference between sotagliflozin 400 mg and glimepiride is zero, 310 patients in the sotagliflozin 400 mg and glimepiride groups will ensure that the upper bound of the 2-sided 95% confidence interval (CI) of the adjusted mean difference is below 0.3% with at least 90% power. This sample size will have 80% power to test the non-inferiority of change of HbA1c from Baseline to Week 52 in completers, with a 30% dropout rate.

A sample size of 310 patients in sotagliflozin 400 mg group and 155 patients in placebo group will have more than 99% power to detect a treatment difference of 0.6% in mean HbA1c change from Baseline to Week 26 between sotagliflozin 400 mg and placebo (SD 1.2%; 2-sided 5% significance level).

A sample size of 155 patients in sotagliflozin 200 mg group and 155 patients in placebo group will have 95% power to detect a treatment difference of 0.5% in mean HbA1c change from Baseline to Week 26 between sotagliflozin 200 mg and placebo (SD 1.2%; 2-sided 5% significance level).

The total sample size is 930 patients to be randomized (sotagliflozin 400 mg group: 310; sotagliflozin 200 mg group: 155; glimepiride: 310; placebo: 155).

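### Is the stated 95% power for sotagliflozin 200 mg against placebo unsound, given that Phase 2b suggests a smaller effect?

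*Protocol*

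**What the plan says.** Protocol section 11.1 gives the planning statement for the lower dose. "A sample size of 155 patients in sotagliflozin 200 mg group and 155 patients in placebo group", it says, "will have 95% power to detect a treatment difference of 0.5% in mean HbA1c change from Baseline to Week 26", the contrast being "between sotagliflozin 200 mg and placebo (SD 1.2%; 2-sided 5% significance level". SAP section 1.3 repeats the claim: "95% power to detect a treatment difference of 0.5% in mean HbA1c change from Baseline to Week 26". Neither document says where 0.5% comes from.

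Protocol section 4.3 reports the Phase 2b dose-ranging study, which ran for 12 weeks. There "the 200 mg dose lowered HbA1c by a mean of 0.48%, while placebo lowered HbA1c by a mean of 0.14" percent; the 400 mg dose lowered it by 0.93%.

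The Week 52 non-inferiority calculation against glimepiride, also in section 11.1, uses a different SD: "Assuming a common standard deviation (SD) of 1.1" percent.

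In the fixed sequence (Protocol 11.4.2.4, SAP 2.4.4.4), "The superiority of sotagliflozin 200 mg compared to placebo on the change in HbA1c from Baseline to Week 26" is seventh of twelve hypotheses. Testing stops at the first result that is not significant. The five that follow are 400 mg against placebo on body weight, on SBP in patients with baseline SBP of at least 130 mmHg and on SBP in all patients; 200 mg non-inferiority to glimepiride; and 400 mg superiority to glimepiride on HbA1c.

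**The concern.** The power statement concerns a between-group difference, so the like-for-like Phase 2b figure is the placebo-adjusted 0.34%. The planning value is 47% above it (0.5/0.34 = 1.47). For 400 mg the plan moves the other way: Phase 2b gives 0.93 − 0.14 = 0.79%, and the plan assumes 0.6%, which is 24% lower (0.6/0.79 = 0.76). The dose with power to spare is planned cautiously and the dose without it optimistically, and no reason is given for either.

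What appears to be at stake is the sequence. A reader takes the risk of stopping at step seven to be about 5%. If the true effect were 0.34%, it would be about 30%, and three later 400 mg comparisons that do not depend scientifically on the 200 mg dose would go untested.

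The two SDs in one section look like a further inconsistency: applying 1.2% to the non-inferiority test would take its power below the stated level.

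**Working it through.** **Inputs.** From Protocol 11.1: 155 per arm ("Patients will be randomized in 2:1:2:1 ratio", so 1:1 for this pair), difference 0.5%, SD 1.2%, two-sided 5%. From Protocol 4.3: 0.48% on 200 mg and 0.14% on placebo at 12 weeks.

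**The plan's own figure.**

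SE = 1.2 × √(2/155) = 0.1363.

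Power ≈ Φ(0.5/0.1363 − 1.96) = Φ(1.71) = 95.6%. A noncentral t calculation gives 95.5%. The stated 95% is therefore right for its inputs; 150 per arm would already reach 95%.

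**At the Phase 2b difference.** 0.48 − 0.14 = 0.34%.

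Power ≈ Φ(0.34/0.1363 − 1.96) = Φ(0.53) = 70.3% (noncentral t: 70.1%).

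**Sensitivity to the true difference** (SD 1.2%, 155 per arm, normal approximation):

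| True difference | Power |
|---|---|
| 0.30% | 59.5% |
| 0.34% | 70.3% |
| 0.40% | 83.5% |
| 0.45% | 91.0% |
| 0.50% | 95.6% |

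**Sensitivity to the SD** (difference 0.34%):

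| SD | Power |
|---|---|
| 1.0% | 84.9% |
| 1.1% | 77.7% |
| 1.2% | 70.3% |
| 1.3% | 63.4% |

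The analysis is an ANCOVA adjusting for baseline HbA1c, strata and country. The documents do not say whether 1.2% is a raw or a residual SD, so the second table matters as much as the first.

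**What designing for 0.34% would have cost.** With SD 1.2%, 80% power needs 196 per arm and 90% needs 262. For the 200 mg and placebo arms together that is 2 × (196 − 155) = 82 or 2 × (262 − 155) = 214 patients on top of 930.

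**The two SDs.** With the stated 1.1%, SE = 1.1 × √(2/310) = 0.0884 and power = Φ(0.3/0.0884 − 1.96) = 92.4%, against a stated figure of at least 90%. For completers, 310 × 0.7 = 217 per arm gives 81%, against a stated 80%. Both hold. Only if 1.2% is carried over do they fall, to about 87.5% and 74%. But 1.2% is stated for Week 26 comparisons with placebo, and the plan never assigns it to the Week 52 comparison with an active drug.

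**The case for a change.** The strongest case for a change is that it would cost only wording. A line justifying 0.5%, or a power range that includes 0.34%, would help readers interpret a failure at step seven and the untested hypotheses behind it. Even 70% may be generous, because the calculation makes no allowance for missing data. As an illustration, suppose 10% of Week 26 values were missing and those patients were credited with no benefit. The difference would shrink to 0.34 × 0.9 = 0.306% and power to about 61%. That pattern fits the placebo-based imputation in the Protocol and the SAP's back-up method. The SAP's main method instead imputes from patients in the same arm who stopped treatment early but were still measured.

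Much of this stands. The arithmetic at 0.34% is right, 0.5% is unexplained, and the two doses do not sit on the same footing relative to Phase 2b.

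Three parts do not stand:

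- **Origin of 0.5%.** That it is the 0.48% change from baseline with placebo left unsubtracted is conjecture. The figures are close, but nothing in the documents links them.
- **A single SD.** Requiring one for all HbA1c calculations is a preference. Different time points and comparators can reasonably carry different planning SDs.
- **Reordering.** Moving the 200 mg test below the three 400 mg tests on weight and SBP would assume that those are nearly certain to succeed. The plan states no power for them and no size for the subgroup with raised SBP. It would also make the 200 mg claim depend on three more tests. And it would alter a prespecified hierarchy after database lock (12 September 2019, SAP section 4), at real cost to credibility.

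**Conclusion.** No change follows. The power statement says what the trial can detect, not what effect is expected, and it is correct as written: about 95.5% at a 0.5% difference.

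The 0.34% benchmark is too weak to overturn that choice. It is a 12-week point estimate with no sample size, SD or interval in the documents, set against a Week 26 endpoint. Protocol section 9.5 says HbA1c reflects the previous 120 days, and 12 weeks is 84 days, so the early value may not show the full effect; the documents do not settle in which direction Week 26 would differ. Over plausible inputs the power runs from about 59% (0.30%, SD 1.2%) to 95.5% (0.50%, SD 1.2%). At 0.34% it runs from 63% to 85% for SDs from 1.3% to 1.0%.

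The consequence is also bounded. The 30% is the marginal risk at one secondary step that is reached only if six earlier tests succeed. A failure there would cost formal claims on five later comparisons, but it would not touch the primary non-inferiority test, the family-wise error rate or any estimate. With enrolment begun on 1 December 2017 and the database locked, restating the power would change no sample size, analysis or decision.

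This is a gap in explanation. An analyst reading a failed step seven can redo the calculation above from figures already in the Protocol.
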